### **Statistical Analysis**

From the screening cohort, the baseline characteristics of the three groups (NAID, IDA, IS) will be compared with descriptive statistics and significance testing. Categorical variables will be compared with a chi-square test and that continuous variables will be compared with an ANOVA (or non-parametric equivalent). For the participants with NAID randomized to treatment or placebo groups, no significance testing will be performed on the baseline characteristics); however, we will note any imbalances that have arisen by chance which may be clinically meaningful. All children with NAID randomized to treatment or placebo will be analyzed in the group to which they were randomized following the intention to treat principle. In the primary analysis, the difference in developmental and hematologic measures in children with NAID randomized to treatment versus placebo will be assessed using linear regression (ANCOVA method) with the initial baseline measures included as the adjusting variable. In a secondary analysis, additional co-variates of clinical or statistical significance (including, parent education, family income) will be included in the model. The primary analysis will be a fixed effects model, ignoring stratification by clinic site. A secondary analysis will include a confirmatory analysis using a mixed effects model with interventions and MSEL scores as the fixed effect and clinic site as the random effects. Although efforts to ensure complete data collection and participant follow up will be maximized, analytic strategies to handle missing data will include imputation techniques, if appropriate. If >20% of participants are lost to follow-up a per protocol analysis will be carried out in addition to the intention to treat analysis.

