**Recruitment Strategy**

TARGet Kids! Network has 6 collaborating primary pediatrician and family medicine practices. This trial will be integrated into the current TARGet Kids data collection system and the baseline data for this trial will be the same data collected during the TARGet Kids! visit of a child. After the physicians receive the lab test results research assistants (RA) will be instructed to contact potential participants over the phone. That the RA can contact TARGet Kids participants over the phone for participation into future studies have been incorporated into the TARGet Kids consent form. When the RA approach the parents over the phone to consider participating in this trial the RA will at the same time introduce the OptEC Trial to the parents and request them to return to the physician's office if they agree to participate. The RAs will be provided with a scripted telephone dialogue in order to standardize the patient recruitment process done over telephone. A Screening Form will be used to screen and enroll participants in the trial. At the physician's office the RA will review the consent form with the parent. The clinic nurse will review the iron status of the child with the parent and obtain informed written consent. The family will have the opportunity to ask questions to the RA, the pediatrician and/or office nurse/staff at any time.

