**Randomization, Stratification, Blocking and Sequence Generation**

Randomization will be stratified by clinic site. Block randomization will be generated with blocks of variable sizes. An advantage of block randomization is that group sizes are similar at the end of each block enrolled. The biostatistician will generate the randomization sequence for each clinic site using computer-generated random numbers.

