**Appendix 2: Subject Recruitment and Data Collection**

Subject recruitment and data collection for children 12-36 months, September 2008 to January 2011:

Site	Date Launched	Number
Village Park Pediatrics	September 2008	626
Clairhurst Pediatrics	August 2008	754
St. Joseph's Family Medicine*	February 2009	2
Mount Sinai Family Medicine*	October 2009	2
Danforth Pediatrics (1st floor)	May 2009	168
Danforth Pediatrics (4th floor)	June 2009	306
St. Michael's Family Medicine	August 2010	7
St. Michael's Ambulatory Pediatric Clinic	To be announced	
Total		1865

\*Discontinued due to poor recruitment rates

Laboratory tests completed for children aged 12-36 months, September 2008 to January 2011:

Laboratory Test	Number	mean	SD	min	max	1st quantile	median	3rd quantile
Hemoglobin g/L	608	122.1	8.84	75	151	117	122	128
Serum Ferritin µg/L	579	28.47	19.13	1.82	138	15.55	23.5	36.7
MCV fL	610	77.91	4.65	55.5	89	75.9	78.4	80.97
C Reactive Protein mg/L	578	1.662	6.70	0.09	122.1	0.2	0.3	0.7

**Trial title: Optimizing Early Child Development in the Primary Care Practice Setting: Pragmatic Randomized Trial of Iron Treatment for Young Children with Non-anemic Iron Deficiency (OptEC)**

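### Randomization is blocked within clinic site but the primary ANCOVA leaves site out; if sites differ after baseline adjustment, the primary interval is mildly too wide

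*Combined protocol and SAP*

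**What the plan says.** The section on randomization states "Randomization will be stratified by clinic site. Block randomization will be generated with blocks of variable sizes", and adds that "The biostatistician will generate the randomization sequence for each clinic site using computer-generated random numbers". Site is therefore a design factor with its own balanced sequence.

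The Statistical Analysis section sets the primary method for the randomized children: "the difference in developmental and hematologic measures in children with NAID randomized to treatment versus placebo will be assessed using linear regression (ANCOVA method", adjusted for the baseline value of the measure. On site it says "The primary analysis will be a fixed effects model, ignoring stratification by clinic site". It gives no reason.

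The same section plans a secondary, confirmatory "mixed effects model with interventions and MSEL scores as the fixed effect and clinic site as the random effects". It does not say that the MSEL scores on the fixed side are the baseline scores, and it names no other outcome. The hematologic measures, which share the primary ANCOVA, and the ECBQ therefore have no site-adjusted analysis.

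On the number of sites, Recruitment Strategy says the "Network has 6 collaborating primary pediatrician and family medicine practices". Appendix 2 lists eight, two of them marked "Discontinued due to poor recruitment rates".

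**The concern.** Blocking within site makes the arms nearly equal in number at every site, so any difference in level between sites largely cancels out of the treatment contrast. The true sampling variance of the estimate then contains only within-site variation. A model without site does not know this: it puts the between-site variation into its residual variance and reports a standard error for a less precise design than the one that was run.

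The error is towards caution. The estimate is not biased and false positives do not increase. What is at stake is a primary confidence interval and p-value that are slightly too conservative, and some power that the design has bought but the primary analysis does not use. All of this depends on sites still differing once baseline MSEL is in the model.

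**Working it through.** **The plan's own figure.** Sample Size gives a 6-point difference, SD 15, 80% power, 5% significance and 75 per group. Two-sided, without baseline adjustment:

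n per group = 2 × (1.960 + 0.842)² × 15² / 6² = 98.1, so 99.

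Multiplying by (1 − r²) for ANCOVA with baseline-to-4-month correlation r = 0.49 gives 98.1 × 0.760 = 74.6, so 75. The documents do not state r; the internal pilot is to estimate it. I assume r = 0.5, which is close to the value that reproduces 150. The missing correlation is a separate matter and does not affect this point.

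**Inputs**
- N = 150, SD 15, difference 6 (Sample Size).
- Six sites (Recruitment Strategy). Their sizes are taken in proportion to Appendix 2 (626, 754, 168, 306, 7), leaving out the two discontinued sites and giving the unlaunched site the smallest count. Scaled to 150, this is about 50/60/13/25/1/1.
- ρ, the site share of 4-month MSEL variance left after baseline adjustment: not in the documents, assumed 0 to 20%.
- Block sizes 2, 4 and 6: assumed, since the plan says only that they vary.

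**Approximate formula.** The ANCOVA standard error with no site effect is 15 × √(1 − 0.25) × √(2/75) = 2.121. With site-blocked allocation:
- true SE ≈ 2.121 × √(1 − ρ);
- SE reported without site ≈ 2.121 × √(1 − ρS), where S is the sum of squared site fractions.

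Here S = (2500 + 3600 + 169 + 625 + 1 + 1)/22500 = 0.306. At ρ = 10% the true SE is 2.121 × √0.900 = 2.012 and the reported SE is 2.121 × √0.9694 = 2.089, which is 3.8% too large. The same formula gives 1.8% at ρ = 5% and 8.3% at ρ = 20%.

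**Simulation.** 15,000 trials per setting, with all models fitted to the same data. The random-site model was fitted by REML with 146 degrees of freedom. For the fixed indicators, the two 1-child sites were pooled with the 13-child site.

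| Residual site share | Power: no site / random site / fixed site (%) | Type I error: no site / random site (%) | Interval without site wider by |
|---|---|---|---|
| 0 | 79.4 / 79.5 / 79.1 | 5.2 / 5.3 | 0.3% |
| 5% | 81.0 / 82.0 / 81.7 | 4.7 / 5.0 | 1.9% |
| 10% | 82.6 / 84.6 / 84.5 | 4.4 / 5.1 | 3.7% |
| 20% | 83.9 / 87.4 / 87.3 | 3.6 / 5.1 | 8.1% |

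Monte Carlo error is about 0.2 points for type I error and 0.3 for power.

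Calibration at 10%: the mean SE without site is 2.093 against a true SD of 2.018; with random site it is 2.017 against 2.017. At 20% the pairs are 2.057 against 1.914, and 1.903 against 1.908.

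**If sites shift baseline and follow-up alike**, baseline adjustment already removes part of the site effect. Power without and with random site is then 80.0 and 80.5% (raw site share 5%), 80.4 and 81.1% (10%), and 81.5 and 83.1% (20%).

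**Separate checks.** A second simulation (2,000 trials per setting) with uneven sites gave intervals 1.9, 3.7 and 7.8% wider at shares of 5, 10 and 20%; with six equal sites, 2.3, 4.4 and 9.9%. A third (6,000 trials per setting, fixed site indicators) gave, without and with site:
- 10% share: type I error 4.3 and 5.1%, power 81.7 and 83.5%;
- 20% share: type I error 3.6 and 5.0%, power 84.5 and 88.3%;
- 0% share: power 79.8 and 79.7%.

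**The case against.** The strongest reply is that nothing here is an error. The plan says openly that the primary model ignores site, and the site-adjusted MSEL result will be produced anyway. Power under the present primary model is 79.4 to 83.9% in the table, so the 80% target is essentially met throughout, and what is forgone lies above it. The documents give no between-site variance. Age-normed MSEL scores and testing by a psychometrist supervised by one developmental psychologist suggest a small residual site effect, and stable differences between practices would be partly absorbed by baseline MSEL. This all stands, and it limits the size of the point.

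It does not remove it. The 80% figure depends on an assumed correlation near 0.5; with no baseline adjustment, 75 per group gives 68.8%. Also, 180 randomized with the plan's upper dropout of 20% leaves 180 × 0.8 = 144, below 150. Power therefore has little slack, and the headline interval and p-value would still come from the less well calibrated model.

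A second reply is that the planned mixed model is not ready to be primary: its covariate is not identified, no estimation method is named, and with about six sites, some very small, the site variance will be poorly estimated. That is fair as a drafting point. If the variance is estimated as zero, the model reduces to the present ANCOVA.

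The site sizes are also proxies: Appendix 2 counts network enrolment at ages 12 to 36 months, not randomized children. The equal-site results show that the conclusion does not depend on them. For hemoglobin and ferritin, one laboratory handles all samples, which removes one source of site difference; no gain was computed for these outcomes or for the ECBQ.

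**Conclusion.** The concern holds as a modest, conditional efficiency point. The randomization balances site and the primary standard error takes no account of it. If sites differ after baseline adjustment, the primary test is mildly conservative: type I error is about 4.7, 4.4 and 3.6% at residual shares of 5, 10 and 20%, and about 1 to 3.5 points of power are forgone. If sites do not differ, nothing measurable is lost either way. There is no bias and no inflated type I error.

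The result rests on an assumed site share, an assumed correlation of 0.5, assumed block sizes, site sizes inferred from Appendix 2, and a two-sided 5% test. The direction follows from the design; the size is uncertain and may be at the low end. The change is worth making because it costs almost nothing.

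**What to change.** In Statistical Analysis, exchange the roles of the two models already there:
- **Primary:** 4-month MSEL with treatment and baseline MSEL as fixed effects and clinic site as a random intercept, fitted by REML with a stated degrees-of-freedom method. Say explicitly that the MSEL covariate is the baseline score.
- **Sensitivity:** the baseline-adjusted ANCOVA without site.
- **Small sites:** the random intercept needs no pooling. State that a zero variance estimate gives the ANCOVA result. If fixed site indicators are preferred, write the pooling rule for small sites beforehand.
- **Other outcomes:** use the same structure for hemoglobin, ferritin and the ECBQ.

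Fix the choice before any unblinded analysis. For hemoglobin and ferritin, that means before Sub-study #2 identifies allocation for the first 40 children.

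The cost is about one sentence, plus one variance parameter with the random intercept, or at most about 5 degrees of freedom out of about 147 with fixed indicators. No extra children or data are needed.

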**Investigational Agent**

Active Arm: Ferrous Sulfate Oral Solution Drops USP (brand Fer-In=Sol by Mead Johnson); Strength: 75mg Ferrous Sulfate/mL = 15mg Fe++/mL; NPN # 00762954; Commercial supply donated in kind by Mead Johnson. Blinded over-labeling will be done by the SickKids Research Support Pharmacy.

Placebo Arm: The placebo is developed by the Hospital for Sick Children Compounding Pharmacy. Contains preserved water (preserved with sodium benzoate), simple syrup NF, denatonium benzoate (for bitter/medicinal taste) and food colouring (see detailed worksheet); similar in colour and taste to active; packaged in 50mL bottles identical to active Fer-in-Sol (empty bottles donated in kind by Mead Johnson).

**Trial title: Optimizing Early Child Development in the Primary Care Practice Setting: Pragmatic Randomized Trial of Iron Treatment for Young Children with Non-anemic Iron Deficiency (OptEC)**

Both active and placebo arms will be packaged in identical bottles with blinded labels. A participant information sheet that contains information regarding the study drug will be provided to parents who agree to participate in the trial.

**Outcomes** – A complete course of iron therapy is 4 months. Changes in developmental and hematologic status may be expected within this time frame. Outcomes will be measured at two time periods: baseline and 4 months after enrollment. The primary outcome will be the developmental score using the Mullen Scales of Early Learning (MSEL). The secondary outcomes will include the behavior measure (Early Childhood Behavior Questionnaire) and two laboratory measures (hemoglobin and serum ferritin levels). The analysis metric will be the mean difference in outcome between the treatment and control groups at 4 month follow up, adjusting for the baseline measures.

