**Blinding**

Parents, attending physicians, laboratory personnel, and study personnel conducting the outcome assessments, data analysts and investigators will be blind to the group allocation. Study medication and placebo will be supplied in bottles that look identical, and the appearance, consistency and taste of the liquid will be similar. Group allocation will be concealed until the final data analysis is performed.

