### **Sample Size**

From previous research, it is anticipated that the mean MSEL developmental score for children with NAID will be 90, and the standard deviation is  $\pm 15$ . To detect a 6 point difference in post-treatment MSEL developmental score between treatment and placebo group, with a power of 80% and a significance level of 5% will require a total sample size of 150 (75 per group).

With an estimated prevalence of NAID of 10%, it is anticipated that screening approximately 1500 children will identify 150 children with NAID to be randomized over a 4 year period.

Expecting potential drop-outs and withdrawals to be 0-20% a total of 180 NAID children will be randomized. For the non-randomized children (IDA and IS), it is anticipated that the mean MSEL developmental score for children with IDA will be 85 and the mean developmental score for IS children will be 100 with a standard deviation of  $\pm 15$ . From the screening cohort of 1500 it is anticipated that 1-2% will have IDA (n=25) and an equal number of randomly selected children with IS (n=25) will be sampled for comparison. To randomly select children with IS, once a child with IDA is identified the immediate next child identified with IS and agrees to participate will be enrolled in the trial.

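### Above 20% loss to follow-up, the only analysis added to unspecified imputation is an undefined per-protocol analysis, which cannot test whether the result depends on lost children's unseen scores

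*Combined protocol and SAP*

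**What the plan says.** All of the relevant analysis text is in the Statistical Analysis section.

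- **Analysis principle.** "All children with NAID randomized to treatment or placebo will be analyzed in the group to which they were randomized", by linear regression (ANCOVA) on the baseline measure.
- **Missing data in general.** "analytic strategies to handle missing data will include imputation techniques, if appropriate". No method, imputation model or criterion for appropriateness follows. The clause carries no threshold, so it also covers loss above 20%.
- **Loss above 20%.** In that case, with that share of "participants are lost to follow-up a per protocol analysis will be carried out in addition to the intention to treat analysis". The term per protocol appears nowhere else. No set is defined and no purpose is stated.

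Three other places bear on the point. The Outcomes paragraph, under Investigational Agent, says: "Outcomes will be measured at two time periods: baseline and 4 months after enrollment". The Sample Size section says: "Expecting potential drop-outs and withdrawals to be 0-20% a total of 180 NAID children will be randomized". The section on patients probably lost to follow-up plans telephone contact on alternate days for a month, then monthly to the end of the trial.

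**The concern.** The plan itself singles out loss above 20% as the situation that needs something extra. What it adds is a type of analysis normally used for adherence, whereas loss to follow-up is a problem of missing outcomes. A child who does not return has no 4-month MSEL, so restricting the data to a per-protocol set cannot recover or vary that child's score.

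At stake is interpretation. Suppose loss is heavy and the estimated difference is near the 6-point target. Agreement between per-protocol and intention-to-treat results could then be taken as reassurance about attrition that it cannot give. The other secondary analyses (extra covariates, and a mixed model with clinic site as a random effect) do not vary the missing-data assumption either.

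**Working it through.** **1. What the per-protocol comparison can show.** There are two outcome times, and a lost child lacks the second. However the per-protocol set is drawn, that child contributes no outcome to it. If the intention-to-treat analysis uses imputation, the two results may differ when loss is explained by measured variables, so the comparison can carry a weak signal of that kind. It carries none about scores that are unobserved given those variables.

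**2. Inputs for scale.** From Sample Size: difference 6, SD 15, 80% power, 5% significance, 75 per group, 180 randomized (90 per arm if split equally). The baseline-to-4-month correlation r is not stated; the internal pilot is to estimate it.

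Reproducing the plan's own figure (two-sided, normal approximation):

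- Without baseline adjustment: n per group = 2 × [15 × (1.960 + 0.842) / 6]² = 98.1, or 99 with the t correction. This is not 75.
- With ANCOVA: 98.1 × (1 − r²) = 75 gives r = 0.485.

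I therefore take r = 0.485 as the reference and show 0.3 and 0.7 as a range.

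**3. Tipping point.** Assumptions: equal loss L in each arm, observed difference 6, and the standard error held at its completer value.

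- SE = 15 × √(1 − r²) × √(2 / [90 × (1 − L)])
- Shift in treated children alone that removes significance = (6 − 1.96 × SE) / L
- If lost placebo children shift k times as far, divide further by (1 − k)

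Worked case, r = 0.485 and L = 0.25: SE = 13.12 × √(2/67.5) = 2.26; 1.96 × SE = 4.43; (6 − 4.43) / 0.25 = 6.3.

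| Loss per arm | r | SE | Treated only | Placebo shifts half as far |
|---|---|---|---|---|
| 20% | 0.485 | 2.19 | 8.6 | 17.1 |
| 25% | 0.485 | 2.26 | 6.3 | 12.6 |
| 30% | 0.485 | 2.34 | 4.7 | 9.5 |
| 25% | 0.3 | 2.46 | 4.7 | 9.4 |
| 25% | 0.7 | 1.84 | 9.5 | 19.1 |

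The 20% row is the boundary; the rule applies only above it. With equal loss and equal shifts (k = 1) the result never tips. With 30% loss on treatment and 20% on placebo (SE 2.26), it tips at 5.2 points if only treated children shift, and at 15.6 if the same shift applies in both arms.

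For scale only, Sample Size anticipates that "the mean MSEL developmental score for children with NAID will be 90" and that "the mean MSEL developmental score for children with IDA will be 85", a gap of 5 points between the two groups.

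**4. Would a per-protocol comparison reveal score-related loss?** Simulation with assumed inputs: no true effect, 90 per arm, 25% lost per arm, 25% non-adherence in both arms, and a per-protocol set made of adherent completers. The simulated baseline correlation is 0.525, slightly above the 0.485 used in step 3.

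- Loss related to the 4-month score in one arm: absolute bias 1.33 for complete-case, 1.29 for per-protocol and 1.28 for imputed intention to treat. The mean gap between per-protocol and imputed results is −0.01, against 0.01 under random loss, so the comparison shows nothing.
- The same score-related loss in both arms: 0.01 or less for all three.
- Loss explained by a measured family covariate in one arm: 0.59 for per-protocol and 0.04 for imputed, a gap of 0.55 (SD 1.45 across trials). This is the weak signal of step 1.

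**The case against.** **Imputation is already planned, and applies above 20% too.** This stands. A reader might infer that a per-protocol analysis is the plan's only answer to missing outcomes; the text does not support that. What remains is that the imputation is conditional and unnamed, and that standard imputation assumes missing at random, so it does not test departures from that assumption.

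**The plan never calls the per-protocol analysis a check on attrition.** Also true. That purpose can be inferred only from the 20% trigger. The fair criticism is that the trigger and the analysis do not match, not that the plan makes a false claim.

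**Harm needs several things at once.** Loss would have to exceed the planned maximum despite repeated calls, depend on unseen scores, and differ by arm, with a result near the margin. On the third condition, parents and attending physicians are blinded, and "study personnel conducting the outcome assessments, data analysts and investigators will be blind to the group allocation". This stands and is why the point is minor.

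**A plausible mechanism may not overturn the result.** In the one-arm score-related simulation, lost children score about 5.0 points below prediction, short of the 6.3-point tipping point at 25% loss. Taking about 1.3 from 6 leaves about 4.7, and 4.7 / 2.26 is about 2.1, still significant. That protection is not general: the tipping point falls to 4.7 at 30% loss, or at 25% loss with r = 0.3.

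**Conclusion.** The point holds as a minor, cheap improvement to the sensitivity analysis. The step tied to loss above 20% cannot show whether the intention-to-treat result depends on lost children's scores, and no other named analysis departs from missing at random.

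A reader might go further and conclude that the primary estimate is biased, or that a positive result would be unsafe. The documents do not support either conclusion. They give no figure for loss by arm or for its relation to score, and the same score-related loss in both arms leaves essentially no bias.

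The size can only be illustrated. Under the assumptions in the working, a treated-only shift of 6.3 points at 25% loss (4.7 to 9.5 for r from 0.3 to 0.7) or 4.7 points at 30% loss removes significance from an observed difference of 6. The shift needed doubles if placebo children move half as far. These are not estimates for this trial, and the textual gap does not depend on them.

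**What to change.** In Statistical Analysis, replace the 20%-triggered per-protocol analysis, as the response to loss, with:

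1. An intention-to-treat ANCOVA with multiple imputation by arm from baseline MSEL, clinic site, parent education and family income.
2. A delta-adjusted (tipping-point) analysis that shifts the imputed MSEL of lost children separately by arm, over a range justified and fixed before unblinding.
3. A report of loss and its reasons by arm.

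Item 2 is the part that tests dependence on unseen scores. Item 1 alone does not: in the score-related simulation, imputation left almost all of the bias.

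If a per-protocol analysis is kept, define its set in advance from adherence, using the returned-bottle volume described under Interventions, and detach it from the loss trigger.

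The cost is revised wording and some extra programming, with no new measurements. The drawback is that a tipping-point analysis yields a range rather than one answer, and its limits must be defended in advance.
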